EORTC	European Organization for Research and Treatment of Cancer
FDA	Food and Drug Administration
FSA	Voluntary Self-Regulation for the Pharmaceutical Industry
GOÄ	German Fee Scale for Physicians
HER2-	Human Epithelial Growth Receptor 2 negative
HR+	Hormone Receptor positive
ITT	Intention to Treat
KBV	National Association of Statutory Health Insurance Physicians
MedDRA	Medical Dictionary for Regulatory Activities
MBOÄ	Professional Regulations for Physicians
mTOR	Mammalian Target of Rapamycin
NIS	Non-Interventional Study
NSAI	Non-Steroidal Aromatase Inhibitors (letrozole, anastrozole)
PEI	Paul Ehrlich Institute
PFS	Progression Free Survival
PFS FU	Progression Free Survival Follow Up
PS	Performance Status
PT	Preferred Term (MedDRA)
p.o.	per os
QLQ	Quality of Life Questionnaire
QoL	Quality of Life
SADR	Serious Adverse Drug Reaction
SAE	Serious Adverse Event
SAP	Statistical Analysis Plan
SDV	Source Data Verification
SOC	System Organ Class (MedDRA)
SOP	Standard Operating Procedure
TTP	Time to Progression
VFA	Association of Research-Based Pharmaceutical Manufacturers

3 Summary

Drugs in this NIS:

Afinitor[®] in combination with exemestane (Aromasin® or generics), in accordance with medical regulations and routine medical practice. Currently the standard dosage is deemed to be 10 mg or 25 mg daily. The treatment can be adjusted at the discretion of the physician based on individual tolerability and clinical necessity according to the recommendations in the respective Summary of Product Characteristics (dose reduction or suspension).

Afinitor[®] is an oral inhibitor of the *mammalian target of rapamycin* (mTOR), which is indicated in combination with exemestane for the treatment of postmenopausal patients with advanced hormone-receptor-positive (HR+), HER2/neu-negative breast cancer without symptomatic visceral metastasis after relapse or progression on non-steroidal aromatase inhibitor (NSAI).

Exemestane belongs to the group of aromatase inhibitors and prevents the synthesis of oestrogens through irreversible binding to the enzyme aromatase. The active substance is indicated for the treatment of advanced breast cancer in post-menopausal women (natural or induced menopause) following progression under anti-oestrogen therapy.

Aims of this non-interventional study:

The aim of this NIS is to acquire information from routine care

- on the impact of physical activity on efficacy and quality of life,
- on prophylaxis and management of stomatitis in routine clinical practice,
- on the sequence of treatment

in the treatment of patients with advanced or metastatic HR+ breast cancer who are treated onlabel with Afinitor[®] und exemestane. Adverse events will be documented.

Number of participating sites:

This non-interventional, multicentre study will be conducted at approx. 400 gynaecology and oncology practices and outpatient clinics scattered throughout the regions in Germany.

Number and selection of patients:

Three thousand postmenopausal women with advanced breast cancer previously treated with a nonsteroidal aromatase inhibitor and currently being treated with Afinitor[®] in accordance with routine practice and the Summary of Product Characteristics will be observed in this non-interventional study.

Patients may be included in this NIS only after being provided with information according to the current Summary of Product Characteristics and after signing the informed consent form.

Observation period:

The planned observation period per patient corresponds to the duration of the treatment with Afinitor[®] and exemestane, but ends no later than the end of the observation phase. This means that the last patient will be observed for a maximum of 12 months. If therapy with Afinitor[®] and exemestane is stopped prior to disease progression, the follow up period will be extended until progression / death of the patient. The observation intervals are not fixed, but are based on current practice and the clinical symptoms of each patient. The end of the treatment with Afinitor[®] and exemestane should be documented regardless of the target interval if treatment is completed before the next follow-up. The reason for discontinuing treatment and the subsequent treatment planned should thus be recorded promptly.

Evaluation parameters:

Expanding knowledge about the course of treatment

Efficacy: To evaluate efficacy, progression-free survival (PFS) is recorded according to the assessment by the treating physician for the total patient group and in relation to intensity of physical activity (subgroup analysis) and duration of treatment.

Quality of life: The following patient questionnaire on quality of life will be completed in hard copy: EORTC QLQ-C30/BR23.

Physical activity: The nature and scope of physical activity before and during treatment with Afinitor[®] and exemestane will be recorded using two questionnaires in hard copy: the "Godin Leisure-Time Exercise Questionnaire" and the "Physical Activity Scales (PAS)¹" developed at the Institute for Cardiovascular Research and Sports Medicine at the Sports University in Cologne.

Stomatitis management: Documentation of the prophylaxis and the management of stomatitis, as well as the start and end dates of this side effect.

Gathering data from clinical practice on the use of drugs

Sequence of treatment: Prior treatment and the treatment following immediately are recorded: type, duration and reason for termination of previous drug treatment(s) and treatment following directly after ending treatment with Afinitor[®].

Drug exposure: Identifying the number of patients in whom treatment needed to be modified, paused or terminated including the type of dose adjustments and the length of and reason for those adjustments.

Safety and tolerability

Documentation of adverse events, serious adverse events, non-serious and serious side

¹ German title: Körperliche Aktivitäts-Skalen (KAS)

effects during routine use.

Scheme of documentation

Time of data entry	At start of documentation	After approx. 2 weeks	Approx. Month 1	Approx. Months 3, 6, 9, 12 etc. at 3- month intervals	At end of treatment with Afinitor [®] and exemestane
Patient characteristics	Х				
Demography and vital parameters	X		X	X	
Medical history and disease characteristics	X				
Previous treatment	Х				
Current tumour history	Х				
Concomitant diseases	Х				
Patient questionnaires on quality of life and physical activity	X		X	X	
Patient questionnaire on stomatitis prevention		Х	Х	Х	
Prescription of Afinitor [®] and exemestane	Х		Х	Х	Х
Prophylactic measures and stomatitis treatment	Х	Х	Х	Х	
Antiresorptive treatment	Х				
Issuance of calendar overview	Х				
AEs/SAEs		Х	Х	Х	Х
Current tumour treatment with Afinitor [®] (dosage, dose reduction, pauses in treatment, reason for dose adjustment)	X	X	X	X	Х
Reason for discontinuing documentation					Х
Reason for discontinuing treatment					Х
Treatment response				Х	Х
Subsequent treatment					Х

Contents of documentation after combination therapy with Afinitor[®] and exemestane

If the treatment with Afinitor[®] and exemestane is stopped prior to disease progression, the following data will be collected approximately every six month until progression or death of the patient:

- Follow up treatment
- Date of progression (if applicable)
- AEs and SAEs with causal connection to Afinitor[®] or exemestane / occurrence of death independent from causal connection (see below) starting day 31 after stopping combination therapy until day 30 after last documentation in the context of PFS follow up visit (last contact

of patient to study centre). All AEs and SAEs with causal connection to Afinitor or exemestane will be documented – inclusive progression with causal connection.

Occurrence of death will be documented independently from causal connection of the combination therapy (Afinitor[®] and exemestane) from day 31 after stopping combination therapy until day 30 after last documentation in the context of PFS follow up visit (last contact of patient to study centre).

Statistical methods:

The NIS will be analyzed using epidemiological methods under primary use of descriptive statistical methods.

Ethical requirements and regulations:

The NIS will be conducted in compliance with the FSA Code of Conduct (dated 07/05/2008, Federal Gazette No. 68, p. 1636) and in accordance with the recommendations of the Federal Institute for Drugs and Medical Devices (BfArM) and the Paul Ehrlich Institute (PEI) on the planning, implementation and evaluation of observational studies dated 07/07/2010 and the VFA recommendations for improving the quality and transparency of non-interventional studies dated 31/01/2007 and 23/04/2007.

Timetable:

The study will be conducted between October 2012 and December 2017.

4 Introduction and rationale

Breast cancer is the **most common cancer** in women. In Europe, breast cancer accounts for approximately 13% of all newly diagnosed cancers and causes approximately 130,000 deaths a year (Boyle et al. 2005).

Approximately 40% of newly diagnosed breast cancer patients develop **metastatic disease**. The treatment of metastatic breast cancer is palliative in nature and focuses on the reduction of tumour size, slowing disease progression and reducing the complications associated with the disease and treatment such as fatigue, bone fractures and hypercalcaemia. The average life expectancy for women with metastatic breast cancer is usually 24 to 30 months (World Health Organization Facts and Figures).

Endocrine therapies are regarded as cornerstones in the treatment of women with advanced hormone-receptor-positive breast cancer. For first-line therapy in postmenopausal patients, non-steroidal aromatase inhibitors (NSAI, e.g. letrozole and anastrozole) feature in the treatment of choice (AGO Guideline 2012). However, some patients do not respond to first-line endocrine therapy (primary or *de novo* resistance), or develop resistance to these substances during the course of

treatment (Johnston et al. 2010).

Resistance to endocrine therapy for breast cancer is known to be frequently associated with an over-activation of the PI3K/AKT/mTOR intracellular signalling pathway. This signalling pathway plays a crucial role in proliferation, survival, angiogenesis and metabolism of cells. In addition, it has been shown that there is a close **interaction between the PI3K/AKT/mTOR and the oestrogen signalling pathways** (Di Cosimo S and Baselga 2010). Thus, the simultaneous inhibition of both signalling pathways constitutes a promising therapeutic principle for overcoming resistance to endocrine therapy. Afinitor[®] is an orally available inhibitor of the *mammalian target of rapamycin* (mTOR), a serine-threonine kinase that is a central component of the PI3K/AKT/mTOR signalling pathway (Baselga et al. 2011).

The efficacy of the combination of an mTOR inhibitor with endocrine therapy has been demonstrated in several clinical trials. In a randomized Phase 2 study comparing **everolimus plus letrozole** with letrozole monotherapy in neo-adjuvant treatment of patients with ER-positive breast cancer, the response rate under combination therapy was significantly higher than letrozole alone (Baselga et al. 2009).

These data were confirmed by the recently announced results of the BOLERO-2 study, an international phase III, placebo-controlled approval study. BOLERO-2 examined the efficacy and safety of **Afinitor® in combination with exemestane** compared to exemestane monotherapy in patients with a previous recurrence or progression during or after letrozole or anastrozole therapy. In the final evaluation after a median follow-up of 18 months, the combination therapy resulted in a significant prolongation of progression-free survival (PFS) from 3.2 to 7.8 months in the local radiological evaluation and reduced the risk of disease progression by 55%. These results were confirmed by an **independent central radiology diagnostic centre (PFS 4.1 vs. 11.0 months, reduction of risk by 62%).** In all subgroups examined, a significant effect in favour of everolimus was observed. The time to deterioration of the quality of life, assessed via patient questionnaires, was significantly longer under the combination therapy. After 18 months' follow-up and 200 documented events, there was a numerical advantage in terms of overall survival in favour of the combination therapy compared with the placebo arm (32.2% vs. 25.4%). The final analysis of overall survival will take place when 398 deaths are documented (Piccard et al. 2012).

Based on the results of the BOLERO-2 study, Afinitor[®] was authorised in combination with exemestane for the treatment of postmenopausal patients with advanced HR-positive, HER2/neunegative breast cancer without symptomatic visceral metastasis in whom a recurrence or progression had occurred following NSAI treatment.

Currently no data are available on the **efficacy** of Afinitor[®] therapy for this indication in **routine use** outside of clinical trials. The product was authorised for this indication in July 2012. The terms of the authorisation permit patients who were not included in the approval study due to their previous treatment or their state of health to receive treatment with Afinitor[®]. This group includes metastatic

9

patients receiving later lines of chemotherapy. It is therefore crucial to gather data on the efficacy of Afinitor[®] in routine care, i.e. outside a strictly controlled clinical study with predefined inclusion and exclusion criteria. These data will make it possible to assess whether the efficacy demonstrated in the approval study is replicated in routine care.

One important objective in the palliative treatment of cancer patients is to enable them to have a good **quality of life** for as long as possible. For this reason, this NIS will examine whether the quality of life under Afinitor[®] changes during the course of treatment. The corresponding questionnaire must be completed by patients in the first and third months after starting treatment and thereafter at 3-month intervals.

The nature and level of physical activity could influence efficacy and/or quality of life of patients with metastatic breast cancer. Such an influence has been shown both for prevention and for the adjuvant setting (Friedensreich 2011). To date however there are hardly any studies that address this issue in metastatic patients. Some data suggest that a **positive effect of physical activity** in women with HR+ breast cancer may be more pronounced than in other breast cancer types (Carmichael et al. 2010). One of the aims of this NIS is to use patient questionnaires to determine the nature and level of physical activity and to investigate a possible correlation with efficacy and quality of life. It will also be used to evaluate whether the fatigue that is present under many therapies can be reduced by physical activity.

Stomatitis is a very common side effect of therapy with Afinitor[®] and exemestane, often occurring soon after starting treatment and frequently regressing during the course of treatment (Porta et al. 2011). In the acute phase, various options are available to the physician to provide relief for the patient. The nature and duration of treatment depend on both the degree of severity of the stomatitis and the specific criteria used by the individual physician. Since the data are as yet unclear, no definitive treatment recommendation for stomatitis under Afinitor[®] can be given. However, stomatitis occurring under treatment with mTOR inhibitors has been seen to differ in nature from the stomatitis that develops under certain chemotherapies. For this reason, this NIS will record the measures used for prophylaxis and, if necessary, treatment of stomatitis and the outcome of these measures.

Various therapeutic options are available for the treatment of postmenopausal patients with metastatic breast cancer. These include both endocrine therapies and chemotherapies (AGO Breast Commission 2012 recommendations). The decision to opt for a particular treatment is taken by the physician in light of the patient's individual situation and in agreement with the patient. In this NIS, prior therapies and therapy following Afinitor[®] and exemestane will be documented. The aim is to document the **sequences of treatment** used in routine practice for combined Afinitor[®] and exemestane therapy.

Afinitor[®] and exemestane are administered on the basis of the respective Summaries of Product Characteristics, guided exclusively by medical and therapeutic necessity.

5 Aims of the study

The aim of this NIS is to acquire information from routine care

- on the impact of physical activity on efficacy and quality of life,
- on prophylaxis and management of stomatitis in routine clinical practice,
- on the sequence of treatment

in the treatment of patients with advanced or metastatic HR+ breast cancer who are treated on-label with Afinitor[®] und exemestane. More specifically, this information includes the following observation parameters:

Primary observation parameters

Evaluation of the efficacy of the combination of Afinitor[®] and exemestane used in routine use in the entire patient group and in relation to the intensity of physical activity. For the subgroup analysis, the treatment courses for patients with higher activity are compared with those patients with lower activity. To evaluate efficacy, PFS under treatment with Afinitor[®] and exemestane is documented according to the assessment of the treating physician.

Secondary observation parameters:

Quality of life and physical activity:

The quality of life of patients during treatment with Afinitor[®] (patient questionnaire EORTC QLQ-C30/BR23) and the importance of physical activity for quality of life.
The nature and level of physical activity are assessed using the "Godin Leisure-Time Exercise Questionnaire" and "Physical Activity Scale (PAS)" questionnaires.

Drug use and treatment sequence:

- Duration of therapy with Afinitor[®] and exemestane in routine medical practice
- Increasing knowledge of routine treatment of breast cancer and of suitable treatment algorithms. For this purpose, prior treatments and the treatment immediately following Afinitor[®] will be documented, in addition to the nature and duration of previous drug treatment(s) and the reason for their discontinuation.
- Number of patients where the treatment needed to be modified, interrupted or discontinued, including type of dosage modifications, duration and cause of the interruptions.

Stomatitis management:

 Prophylaxis and treatment of stomatitis as an adverse event during routine use of Afinitor[®] in combination with exemestane and concomitant treatments, as well as the start and end dates.

Documentation of adverse events (AEs).

6 Study design

This is a non-interventional study pursuant to Section 4 para. 23 sentence 3 AMG, "in the framework of which information from the treatment of persons with drugs is analysed using epidemiological methods; treatment including diagnosis and monitoring shall be provided strictly in accordance with medical practice, not in accordance with a fixed study protocol; if the study drug is subject to authorization or approval pursuant to Section 21a para. 1, treatment shall also be provided in accordance with the instructions for use specified in the authorization or approval" and is conducted in line with the FSA Code of Conduct and according to the joint recommendations of BfArM and PEI on the planning, conduct and analysis of observational studies as well as the VRA recommendations on improving the quality and transparency of non-interventional studies.

The design of an NIS allows observation without the need to specify strict inclusion and exclusion criteria or interventions. It is therefore suitable for the study aims described, in particular because no requirements regarding the nature and level of physical activity are specified, likewise in relation to prophylaxis and management of stomatitis. Instead, the intention is to describe in a relatively large number of patients the routine medical treatment and the real activity situation in patient's everyday life. In this NIS, the course of treatment is also documented for those patients who were treated on-label with Afinitor[®], but were not included in the approval study due to previous treatment or their state of health.

6.1 Study sites and patients

This non-interventional, multicentre study will be conducted at approx. 400 gynaecology and oncology practices/clinics. The participating physicians will be informed of the aims and modalities of this NIS by the medical director of the NIS. The field employees of Novartis Pharma GmbH will be deployed for administrative purposes in the conduct of the NIS and will distribute all documentation materials to the participating sites.

There will be prospective documentation of the course of treatment for a total of approx. 3000 patients treated with Afinitor[®] in combination with exemestane according to routine practice and the respective Summaries of Product Characteristics. Patients may also be included in the documentation if treatment with Afinitor[®] and exemestane was started a maximum of 6 weeks before they gave their consent to participate in this NIS and they are currently receiving Afinitor[®] and exemestane. The planned observation period per patient corresponds with the duration of treatment with Afinitor[®] in combination with exemestane, but ends on completion of the observation phase. This means that the last patient will be observed for a maximum of 12 months. If the therapy with Afinitor[®] and exemestane is stopped prior to disease progression, the follow up period will be extended until time of progression / death of the patient. Observation intervals are not specified, but will be guided by current practice and the clinical symptoms of the respective patient, e.g. after approx. 2 weeks, 1 and 3 months and then at 3-month intervals (6, 9, 12 ... etc.) after the start of

treatment with Afinitor[®] and exemestane. The end of this treatment should be documented regardless of the target interval if treatment is ended before the next regularly scheduled follow-up.

The following patients are suitable for inclusion in this NIS:

- Patients who are treated with Afinitor[®] plus exemestane according to routine practice and the Summary of Product Characteristics or for whom treatment with Afinitor[®] and exemestane is indicated.
- Postmenopausal women with advanced hormone-receptor-positive, HER2/neunegative breast cancer without symptomatic visceral metastases.
- Recurrence or progression after a non-steroidal aromatase inhibitor (e.g. anastrozole, letrozole)
- ✓ Age ≥ 18 years
- Patients who were given information about this NIS and signed an informed consent form.

There are no exclusion criteria except the contraindications listed in the Summary of Product Characteristics. Participating patients may not take part in any clinical study in parallel to this, as this does not constitute routine medical practice and is therefore counter to the aims of an NIS pursuant to Section 4 para. 23 sentence 3 AMG.

Notes on the indication for Afinitor[®] and exemestane and contraindications and possible side effects are provided in the enclosed Summary of Product Characteristics. Treatment may not be administered for the purpose of inclusion in the NIS, but must be given exclusively for the purpose medical and therapeutic need.

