6.4 Observation parameters

In this non-interventional study, diagnostic measures and medically indicated examinations are documented only if they were conducted in accordance with normal routine practice. The points described under 6.4.1 to 6.4.3 are guideline observation parameters and are solely for the purpose of orientation.

Optional intermediate examinations can be anticipated per patient corresponding to routine practice in normal conditions. Findings are to be documented at the time of inclusion and after approx. 2 weeks, 1, 3, 6, 9, 12... etc. months until the end of treatment with Afinitor[®] and exemestane or until the end of the observation phase, whichever occurs first.

To assess quality of life and physical activity before the start of treatment and during treatment, questionnaires in hard copy will be provided. To estimate patient compliance, patients will be given calendar overviews.

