6.4.1 Observation parameters at the initial examination

Prerequisite: written consent form for participation in the study

- Date of start of observation/initial examination
- Patient history, demographic data, and characteristics of the disease
 - Date and characteristics of the initial diagnosis (month/year, tumour stage (TNM), grading, histological subtype, Ki67)
 - Diagnosis-specific history at the first evidence of metastasis (date, type of metastasis, location)
 - Previous and current treatment (radiotherapy, pharmacological treatment with start, end, and best result observed with respect to tumour response)
 - Details of previous tumour resection and metastases and their tumour biology if available
- ECOG performance status if conducted
- Height, weight
- Current tumour status (TNM stage, location of metastases and latest imaging (CT, MRI, ultrasound, bone scintigraphy, etc.))
- Reason for switching to Afinitor[®] (progression, patient wish, not progression-induced switch)
- Comorbidity
- Antiresorptive treatment to prevent bone-related complications if bone metastases are present
- Planned prophylactic measures against stomatitis
- Quality of life: patient questionnaire EORTC QLQ-C30/BR23
- Physical activity: "Godin Leisure-Time Exercise Questionnaire" and "Physical Activity Scale" (PAS)
- Compliance: calendar overview provided to estimate treatment compliance
- Prescription for Afinitor[®] (date, dosage, pack size)
- Planned follow-up visit

6.4.2 Observation parameters two weeks after the start of documentation (prospectively after implementation of Amendment 2 in the eCRF)

If a visit takes place approx. 2 weeks after the start of documentation in accordance with routine practice, the following observation parameters are documented at this time:

- Date of follow-up
- Documentation of stomatitis treatment if any was needed and given
- Current tumour treatment with Afinitor[®] (dosage, dose reduction, treatment breaks, reason for dose adjustment)
- Patient questionnaire on stomatitis prophylaxis
- Documentation of adverse events
- Next scheduled follow-up

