12.2 Descriptive statistical methods

Variables reaching at least interval level will be presented in tabular form including their sample values (number of valid and missing values, minimum, maximum, 5th percentile, first quartile, third quartile, 95th percentile, median, mean, standard deviation).

For variables at the nominal and ordinal level, distribution of the absolute and relative frequencies will be indicated.

For adverse events, incidences will be reported based on the patient population included and incidence density (number of events/sum of person times in years) according to the MedDRA system organ class and preferred term for adverse events (AEs), serious adverse events (SAEs), adverse drug reactions (ADRs) and serious adverse drug reactions (SADRs). Times of events and survival time analyses will be analysed using the Kaplan-Meier methodology. The derivation and rating of these event times is described in the SAP.

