12.4 Analysis sets

The analysis is based on the population of patients with documented administration/prescription of Afinitor[®] for whom at least one follow-up under treatment is available.

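### Entry up to 6 weeks after treatment start makes some baseline questionnaires on-treatment, puts the 2-week visit on two clocks, and biases PFS upward if pre-consent time counts as time at risk

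*Protocol*

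**What the plan says.** Protocol Section 6.1 allows documentation of patients whose treatment "was started a maximum of 6 weeks before they gave their consent to participate in this NIS", on condition that "they are currently receiving Afinitor[®] and exemestane". The same section gives example visit times (about 2 weeks, 1 month, 3 months, then quarterly) counted from the start of treatment.

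Section 6.4 gives the purpose of the questionnaires: "To assess quality of life and physical activity before the start of treatment and during treatment". Section 6.4.1 makes written consent a prerequisite for the initial examination, at which they are first completed. Section 6.4.2 places the next visit "two weeks after the start of documentation".

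On stomatitis, Section 4 describes it as "often occurring soon after starting treatment and frequently regressing during the course of treatment". Section 7.1 has adverse events recorded from the first administration. The documentation scheme in Section 3 marks adverse events at every time except the start of documentation, although its row for prophylaxis and stomatitis treatment is marked there.

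On efficacy, Section 5 says: "To evaluate efficacy, PFS under treatment with Afinitor[®] and exemestane is documented according to the assessment of the treating physician". Section 12.2 says: "Times of events and survival time analyses will be analysed using the Kaplan-Meier methodology", and its next sentence leaves the derivation of event times to the SAP.

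**The concern.** Late entrants are selected for still being on both drugs. Anyone who progressed, died or stopped between first dose and the time of possible consent cannot come in by this route. Four things are at stake.

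- **Baseline.** A late entrant has no pre-treatment questionnaire, and no later analysis can recover one. Section 4 wants to know whether quality of life changes during treatment, and the primary parameter includes PFS by intensity of activity. If the first questionnaire sets the activity group, the grouping may already reflect early toxicity.
- **Visit clock.** The same visit label means different times since first dose for different patients.
- **Early stomatitis.** By the protocol's own account it tends to come soon after treatment starts, which is the period a late entrant has partly passed before documentation begins.
- **PFS.** Weeks that a patient had to survive event-free in order to be enrolled would be credited as follow-up if the clock starts at first dose and delayed entry is ignored. Section 4 wants to judge whether the approval study's efficacy is replicated in routine care, so an upward shift would matter.

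**Working it through.** **Passages side by side**

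1. *Questionnaires.* Consent may come up to 6 weeks after first dose (6.1), and the initial examination with its questionnaires requires consent (6.4.1). A late entrant's first questionnaire is therefore on-treatment, against the stated purpose in 6.4.
2. *Clock.* For a patient entering at week 6, the visit in 6.4.2 falls at about 6 + 2 = 8 weeks after first dose. By the count in 6.1 it belongs at week 2, which has already passed.
3. *Adverse events.* Section 7.1 covers the time from first administration. Neither the scheme's adverse-event row nor the list in 6.4.1 prompts for events at the start visit, so events before entry depend on recall or the chart.

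**Size of the conditional PFS effect**

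The protocol has no figure of its own for this, so there is none to reproduce.

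Inputs from the protocol: reference median PFS 7.8 months by local evaluation (Section 6.3); window 6 weeks = 42/30.4375 = 1.38 months; about 3000 patients.

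Assumptions, not in the protocol: exponential PFS; a share f of starters intended for late entry; lag L uniform on 0 to d = 1.38 months; PFS timed from first dose with everyone counted at risk from time zero.

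- Hazard: λ = ln 2 / 7.8 = 0.0889 per month, so λd = 0.1226.
- Events within 6 weeks: 1 − exp(−0.1226) = 11.5%.
- Mean chance of being event-free at the lag: m = (1 − exp(−λd))/(λd) = 0.1154/0.1226 = 0.941.
- For t > d the naive curve is exp(−λt)/D with D = (1 − f) + f·m. The naive median is 7.8 − ln(D)/λ.

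| f | D | Naive median (months) |
|---|---|---|
| 10% | 0.994 | 7.87 |
| 25% | 0.985 | 7.97 |
| 50% | 0.971 | 8.14 |
| 100% | 0.941 | 8.48 |

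The extreme case, everyone entering exactly at week 6, gives 7.8 + 1.38 = 9.18 months. For scale, the standard error of a Kaplan-Meier median at n = 3000 without censoring is 0.5/(√3000 × 0.5λ) = 0.21 months.

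**Fewer detected early events.** Section 6.4.3 has no imaging at month 1, so 11.5% is probably too high. If only a share p of patients has a detected event before week 6 and everyone enters at week 6, the naive median is 7.8 − ln(1 − p)/λ, with the curve near the median unchanged. This gives 7.91 months at p = 1% and 8.03 at p = 2%.

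**Does the remedy work?** In a simulation with f = 50% and uniform lags, the naive Kaplan-Meier median was 8.12 months. With entry to the risk set at consent it was 7.78, against a true 7.8.

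**The case against.** The strongest reply is that the protocol does not fix the error in PFS. It names neither a time origin nor a rule for entry to the risk set, it sends event-time derivation to the SAP, and Kaplan-Meier methodology does not exclude delayed entry. With the clock at consent, the same exponential model returns 7.80 months, although the origin then differs from treatment start by up to 6 weeks. A reader might infer from the entry rule that PFS is overstated. The protocol supports only that it would be under one analysis choice. The size is also open: the late share is not given, a constant hazard from day 0 fits poorly with no imaging at month 1, and at 25% late entrants the shift of 0.17 months is below one standard error. The analysis-set rule in Section 12.4, which keeps only patients "for whom at least one follow-up under treatment is available", is a separate selection and is not counted here.

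A reader might also infer that early stomatitis is missed. The protocol contradicts that for enrolled patients: Section 7.1 records events from first administration with their first occurrence and duration, start and end dates of stomatitis are documented, and the scheme marks stomatitis treatment at the start visit. What remains is dependence on recall or chart, and patients who stopped before they could consent.

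Finally, visit intervals are for orientation only, the 2-week entry applies only if a visit takes place, results are declared purely descriptive, and no passage says that the first questionnaire defines the activity groups. All this limits the weight of the point. It does not resolve the contradiction over the questionnaires or the two clocks.

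**Conclusion.** The point holds in limited form. Certain from the text, and independent of any SAP: late entrants' first questionnaires cannot be pre-treatment measurements; Sections 6.1 and 6.4.2 count the 2-week visit from different starts, up to 6 weeks apart; and the start visit has no adverse-event entry although recording reaches back to first dose.

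Conditional: an upward bias in median PFS, only if time runs from first dose with patients at risk before consent. Under a constant hazard, true median 7.8 months and uniform lags, the naive median is about 8.0 to 8.5 months at 25% to 100% late entrants. It is likely smaller in practice, because few events can be detected before week 6. No bias in the comparison of higher with lower activity has been shown, only that its baseline may be measured on treatment. The number of patients affected is unknown.

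**What to change.** - **PFS.** State that PFS runs from first dose and that patients enter the risk set at consent (left-truncated Kaplan-Meier, and Cox with delayed entry where a model is used). Alternatively, add a sensitivity analysis in patients enrolled on or before first dose. Delayed entry does not bring back patients who stopped treatment before consent, so it assumes that they do not differ in prognosis.
- **Questionnaires.** Flag first questionnaires completed after first dose, analyse them as post-baseline at their actual time, and leave them out of change-from-baseline analyses and baseline-activity grouping.
- **Adverse events.** Add a prompt at the start visit for adverse events, including stomatitis, since first dose.
- **Clock.** Reconcile Sections 6.1 and 6.4.2, and analyse by actual time since first dose. Imposing fixed visit windows would suit a non-interventional study poorly.

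The cost is wording in Sections 6.1, 6.4, 6.4.2 and 12.2, the documentation scheme, and one eCRF prompt. Section 6.4.1 already lists the start of current drug treatment and the date of start of observation. The consent date is not listed as an item and should be added. The downside is a smaller set for baseline-dependent comparisons.
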